7.3.2.3 Baseline Assessment

Demographics. Demographic and other pertinent information, including assistance received, adaptive equipment usage, and falls, will be collected.

OARS ADL scale. The OARS ADL scale^[51] will be used to screen for functional performance. The OARS ADL has been validated for the older adult ED population^[52], is brief and easy to administer. Potential participants are asked about their ability to perform each of 14 activities. Responses are scored on a 0-2 scale, with higher scores indicating greater independence. Individuals who receive a score of 0 on one or more activities or a score of 1 on two or more activities will qualify for the study.

Falls Efficacy Scale-International (FES-I). The Falls Efficacy Scale-International (FES-I)^[53] will be used to assess participants’ self-efficacy in performing daily activities without falling. The FES-I has good test-retest reliability and validity and consists of a list of 16 daily activities (e.g., getting in and out of bed) on which respondents rate their confidence doing each activity without falling on a scale from 1 (very confident) to 10 (no confidence at all). Total FES-I score is the sum of each activity score, with higher scores indicating greater fear of falling.

Patient Reported Outcomes Measurement Information System (PROMIS) Global Scale. Self-rated health will be measured using the Patient Reported Outcomes Measurement Information System (PROMIS) Global Scale^[54] which measures general perceptions of health. We will use two scales: global physical health (overall physical health, physical function, pain, and fatigue) and global mental health (quality of life, mental health, satisfaction with social activities, and emotional problems). Reliability and validity of the scales have been established^[54, 55].

Westmead Home Safety Assessment (WeHSA). The Westmead Home Safety Assessment (WeHSA)^[57] will be used to identify the number of environmental hazards in all areas of the home (e.g., seating, bedroom, medication management) via 72 categories. Each category is specified with explicit descriptors to qualify a given hazard with a score of 0 for absent and 1 for present. Total hazards are summed.

Short Michigan Alcoholism Screening Test – Geriatric Version (S-MAST-G). The S-MAST-G^[58] will be used to screen for the presence of an alcohol problem in potential participants. The S-MAST-G has been validated for the older adult population^[59]. Potential participants will answer 10 yes/no questions about their alcohol consumption in the past year; two or more “yes” responses indicate a likely alcohol problem..

Geriatric Depression Scale Short Form (GDS-SF). The GDS-SF^[60] will be used to assess depression levels in participants. The GDS-SF is a 15-item self-report questionnaire specifically designed and validated with the older population, and correlates highly with the original 30-item GDS ($r=.84$)^[60]. Participants answer yes-or-no questions about their feelings in the past week. Total scores range from 0 to 15, and scores of 5 or more indicate probable depression.

Short Blessed Test (SBT). The SBT^[61] will be used to screen for severe cognitive impairment. The SBT has good validity for older adults^[61] and correlates well with the Mini-Mental State Exam^[62]. This brief, six-item questionnaire assesses cognition, memory, and orientation. Incorrect items are scored as the product of the number of errors made and a weighting factor; the sum of incorrect item scores comprises the total score. Total scores range from 0-28; scores of 10 or more are consistent with dementia and other cognitive difficulties. Individuals who receive a SBT score 10 or more will not be allowed to participate in the proposed study.

Prescription medications. A medication inventory will be collected.

Performance Oriented Mobility Assessment (POMA). Mobility and balance will be assessed using the Performance Oriented Mobility Assessment (POMA)^[63], a task-oriented gait and balance assessment that has been validated for the older adult population.

Strength, and range of motion of the upper extremity. Strength and range of motion of the upper extremity will be assessed using group muscle tests and goniometry and scored as within normal limits, within functional limits, or impaired^[64]. Strength of the dominant hand will be assessed using a dynamometer.

Pelli-Robson. We will measure visual contrast sensitivity using the Pelli-Robson test^[65]. We will score participants’ binocular contrast sensitivity letter by letter.

Falls behavioral Scale for Older People (FaB). Protective behavioral factors to prevent falls will be assessed using the FaB. This instrument includes ten behavioral dimensions: cognitive adaptations, protective mobility, avoidance, awareness, pace, practical strategies, displacing activities, being observant, changes in level, and getting to the phone^[66].

7.3.3 Intervention and follow up sessions

7.3.3.1 Intervention

Participants randomized to the intervention group will receive the intervention over 2 visits and one booster session at 6 months according to a manualized intervention. Briefly, for the intervention group, the occupational therapist will begin the intervention during the WeHSA. During the WeHSA the occupational therapist will assist the older adult to identify home hazards, work through potential solutions to reduce or remove the hazard, if possible, implement solutions (such as removing a throw rug), create plan for additional hazard removal, begin self-management training for behavioral and environmental fall risks, and provide training to complete the calendar journal. Between visits, the occupational therapist will assist the older adult to obtain equipment or home modifications. At the second visit, the occupational therapist will provide any necessary installation of equipment (such as a tub transfer bench), explain the purpose of each new equipment, teach techniques to safely use the equipment, and observe the older adult safely using the equipment. The occupational therapist will also continue the self-management training to improve daily activity performance and safety.

7.3.3.2 5 month adherence

A phone call to evaluate adherence will be made at approximately five months (in anticipation of the 6 month booster session).

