7.3.3.4 Monthly monitoring falls

To record falls, an individually customized calendar journal will be designed for each participant for daily recording of falls^[48]. Our method of tailoring the calendar journal includes life event date anchors, incentives and personalization^[49], we will construct the participant-tailored calendar journals^[50]. There will be space to record the primary outcome of falls (fall or no fall) each day. If a participant falls, they will be instructed to complete a fall form. Calendar journal pages and fall forms will be collected monthly via U.S. mail. Falls will be verified with a follow-up telephone interview by a community coordinator.

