7.4.6 Cost

The cost of the treatment will be measured by tracking cost of modifications and adaptive equipment for each participant. This will be tracked using the Invoice Form which includes both

costs from the contractor as well as costs of any equipment ordered from a medical supply company or obtained from a community resource (medical equipment lending program). The total amount of money spent on each person will be tracked on this form.

7.5 Overview of study assessments by time point.

	Phone Screening	Consent visit	Baseline assessment	Treatment session (tx group only)	Follow-up months 1-12	5 month phone call (tx group only)	6 month Booster in home (tx group only)	12 month phone call
Consent		x						
Calendar Questionnaire		x						
Demographics		x						
WeHSA			x	x			x	
SMAST-G			x					
GDS		x						
SBT	x							
Medication		x						
ROM			x					
Strength			x					
Grip Strength			x					
Near Visual Acuity			x					
Contrast Sensitivity			x					
POMA			x					
Falls			x	x	x			x
OARS			x					x
FES		x						x
PROMIS		x						x
Falls behavioral Scale		x						x
Fidelity to treatment (visit by visit grid)			x	x			x	
Time (Dose), Completion of Session, Cost				x			x	
Adherence						x	x	x

*randomization before T1

*both groups will send in monthly fall journal information

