10 STATISTICAL CONSIDERATIONS

9.1 Sample Size and Randomization

Power computations reflect two general principles. The first is that we will be conservative by underestimating and overstating power. Second, estimates of statistical power will be consistent with the method of analyses. Our primary outcome is time to event; therefore, we will determine the sample size and power within the survival data analyses framework. The Cumming et al.⁷⁹ sample is most similar to our target sample and similar regarding the method of fall ascertainment using daily calendars. On this basis, we assume that approximately 61% of control group participants will fall during 1 year of follow-up. For a meaningful reduction in fall risk, an intervention needs to demonstrate at least 30% reduction in falls.^{105, 106} The Cochrane Review of interventions for preventing falls in older, community-dwelling adults reported that randomized trials of home-safety interventions and personal mobility aids reduced the rate of falls (RaR, 0.59; 95% CI, 0.42–0.82) among high-risk participants defined as having a history of falling or other risk factor for falls.³⁰ Another meta-analysis²⁸ of four randomized trials of environmental interventions, which included some of the same studies as the Cochrane Review, reported a 39% reduction in the risk of falls in high-risk populations, defined as a history of falling in the past year or presence of other risk factors for falling. Because our target sample can be defined as “high risk,” and because our intervention can be defined as a high-intensity home modification, we project a 30% or greater reduction in fall risk at 12 months after treatment. Figure 6 displays the power as a function of total sample size given a fall rate of 42% (event-free rate of 0.58) in the intervention group and a fall rate of 0.61 (event-free rate of 0.39) in the control group, with a 20% attrition rate. A two-sided log-rank test with an overall sample size of 300 participants (150 in each group) achieves 84% power at a 0.05 significance level to detect a difference of 0.19 between 0.39 and 0.58—the proportions without falls in the control and intervention groups, respectively. This corresponds to a hazard ratio of 0.5785 of fall in intervention versus control groups. These results are based on the assumption that the hazard rates are proportional.

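### Calendar-journal training is documented only for the intervention arm, which also has extra contacts that ask about falls: a risk of differential fall reporting, in a direction the documents do not settle

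*Combined protocol and SAP*

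**What the plan says.** Section 7.3.3.4 gives each participant a tailored journal with a daily fall entry. Anyone who falls fills in a fall form, "Calendar journal pages and fall forms will be collected monthly via U.S. mail", and a coordinator verifies reported falls by telephone. A footnote to the 7.5 schedule confirms that both groups send in journals, and 7.2 gives everyone a 12-month call.

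Section 7.3.3.1 describes the therapist's home-hazard visit for the intervention group. Among the therapist's tasks there is to "provide training to complete the calendar journal". No section describes journal training for controls.

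In the 7.5 schedule, the Falls row is marked at baseline, at "Treatment session (tx group only)", at follow-up months 1-12 and at the 12-month call. Section 7.4.5 adds a self-report Fall Form at a 6-month follow-up visit. Section 7.2 says that controls have no 6-month assessment.

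Section 10.3 makes time to first fall over 12 months the primary outcome, counted from completion of the intervention. Total and injurious falls are secondary. Section 2.1 includes a safety hypothesis that falls are no more frequent than under usual care.

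**The concern.** A diary outcome depends on how well participants understand what counts as a fall, how faithfully they record it, and how often someone prompts them. If one arm is trained in the diary by a therapist and asked about falls more often, the arms may differ in the share of falls recorded as well as in the falls that occur. Verification does not repair this, because 7.3.3.4 describes a call about reported falls and no search for unreported ones. Neither the log-rank test nor the covariate-adjusted Cox model can separate a reporting difference from a treatment effect.

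If training and prompting raise recording in the intervention arm, the hazard ratio moves toward 1 and a real benefit may be missed or look like harm. If unblinded participants who have worked with a therapist on preventing falls are less ready to report them, the bias favours the intervention.

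**Working it through.** **1. What each arm gets, as written**

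| Item | Intervention | Control | Section |
|---|---|---|---|
| Tailored daily journal, mailed monthly | yes | yes | 7.3.3.4, 7.5 |
| Verification call after a reported fall | yes | yes | 7.3.3.4 |
| 12-month call | yes | yes | 7.2, 7.5 |
| Calendar Questionnaire at consent (content not described) | yes | yes | 7.5 |
| Journal training | yes | not described | 7.3.3.1 |
| Falls asked at treatment session | yes | no such contact | 7.5 |
| Fall Form at 6-month visit | yes | no 6-month assessment | 7.4.5, 7.2 |

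The 6-month booster column in 7.5 has no Falls mark, so 7.5 and 7.4.5 do not agree on whether falls are asked about at that visit.

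**2. The plan's own power figure**

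Inputs, all from 9.1 Sample Size and Randomization: "a fall rate of 0.61 (event-free rate of 0.39) in the control group"; "a fall rate of 42% (event-free rate of 0.58) in the intervention group"; 300 participants, 150 per arm; "with a 20% attrition rate"; two-sided 0.05.

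- HR = ln(0.58)/ln(0.39) = 0.5785.
- After attrition: 300 × 0.8 = 240, or 120 per arm. Events E = 120 × (0.61 + 0.42) = 123.6.
- Freedman: power = Φ(√E × |1 − HR|/(1 + HR) − 1.96) = Φ(11.118 × 0.2670 − 1.96) = Φ(1.009) = 0.843.

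This reproduces the statement that the design "achieves 84% power at a 0.05 significance level". There is no arithmetic error in the plan here.

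**3. Illustrations under assumed capture rates**

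The documents give no capture rate by arm; the 99% in section 4 is a journal response rate in previous studies. Two scales are shown for a capture share c and true 12-month risk p:

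- *Hazard scale*: each fall is recorded independently with probability c, at constant hazard, so a repeat faller can still be caught later. Observed risk = 1 − (1 − p)^c.
- *Faller scale*: a share 1 − c of fallers is missed altogether. Observed risk = c × p.

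In each case HR = ln(1 − p_int)/ln(1 − p_ctl), E = 120 × (p_int + p_ctl), and the Freedman formula applies.

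Example, 99% intervention and 90% control, hazard scale: p_ctl = 1 − 0.39^0.90 = 0.571; p_int = 1 − 0.58^0.99 = 0.417; HR = 0.5785 × 0.99/0.90 = 0.636; E = 118.6; power = Φ(2.420 − 1.96) = 0.677.

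| Capture, intervention / control | Hazard scale: HR, power | Faller scale: HR, power |
|---|---|---|
| 100% / 100% (plan) | 0.579, 0.843 | 0.579, 0.843 |
| 99% / 95% | 0.603, 0.778 | 0.621, 0.726 |
| 99% / 90% | 0.636, 0.677 | 0.675, 0.551 |
| 90% / 90% | 0.579, 0.817 | 0.596, 0.760 |
| 90% / 100% | 0.521, 0.932 | 0.504, 0.948 |

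The 90%/90% row shows that some of the loss under 99%/90% comes from missing falls at all and not from the difference between arms. The last row is not a gain: the higher rejection rate comes with an exaggerated effect.

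**4. No true effect (0.61 in both arms)**

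Faller scale, 120 per arm, two-proportion normal approximation, 100% intervention and 90% control capture:

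- Observed risks 0.61 and 0.549; HR = ln(0.39)/ln(0.451) = 1.18.
- Difference (control − intervention) = −0.061. Pooled risk = 0.5795, null SE = √(2 × 0.5795 × 0.4205/120) = 0.0637. Unpooled SE = √((0.549 × 0.451 + 0.61 × 0.39)/120) = 0.0636.
- Chance of falsely favouring control = Φ((−1.96 × 0.0637 + 0.061)/0.0636) ≈ 0.16, against a nominal 0.025.

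With the capture rates exchanged, the observed HR is 0.85 and the chance of falsely favouring the intervention is about 0.16.

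**The case against.** The strongest reply is that the outcome instrument is shared. Both arms have the same journal, mailing, verification and 12-month call. A reader might infer from the training sentence that the primary outcome is measured differently in the two arms. The documents do not support that; they show one instrument with uneven preparation and prompting, which is a risk and not a demonstrated difference.

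Second, controls are not left without instruction. Section 5.2 promises a scripted discussion of follow-up procedures at consent, and 7.3.2.1 promises a plain-language account of what is expected. The therapist's visit is described only in brief, and a manual of procedures not included here may train controls. This stands as a reason for caution. But neither consent passage mentions training in the journal, and if the manual already covers it, one sentence in the protocol settles the matter.

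Third, time zero in 10.3 is completion of the intervention, so falls reported at the initial treatment sessions largely precede the primary follow-up period. This also stands, and it weakens the treatment-session mark for the primary outcome. It does not touch the training, whose effect would last through follow-up. The 6-month Fall Form falls inside follow-up if completion means the initial visits. If the booster counts as part of the intervention, that form would look back at falls before time zero. The plan does not say which, nor which sources feed each fall outcome.

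Fourth, the capture rates and the direction are assumed. This is accepted: a reader might take the 68% as the trial's real power, and nothing in the documents supports that.

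**Conclusion.** The concern holds as a documented imbalance in journal training and fall enquiries, with a resulting risk of differential reporting. It bears on time to first fall, on total falls and on the safety comparison of fall rates. It does not show that the arms use different outcome measures, that controls are in fact untrained, or that power has been lost.

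The illustrations show that the design is sensitive: a gap of 4 to 9 percentage points against control puts power between about 78% and 55%, depending on the scale, while a 10-point gap the other way gives a hazard ratio of 0.50 to 0.52. They assume proportional hazards, 240 evaluable participants and capture rates that are not in the documents. The change is worth making because it is cheap and because no analysis can remove the ambiguity afterwards.

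**What to change.** 1. Give every participant the same scripted journal training, from the same staff, before allocation. The consent visit is the natural place. If the tailored journal is not yet built then, use one common script for both arms when it is issued.
2. Remove journal training from 7.3.3.1.
3. State in 10.3 that the primary, secondary and between-arm safety fall outcomes come only from journals, mailed fall forms, verification calls and the 12-month call. Falls known only from treatment sessions or the 6-month visit are not counted in these comparisons.
4. Reconcile 7.4.5 with 7.2 and the 7.5 schedule on the 6-month Fall Form.
5. If the manual of procedures already trains controls in the same way, say so in the protocol.

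The cost is protocol wording and a few minutes of training per participant, possibly at a separate contact if the journal is issued after consent. The small downside is that a fall mentioned only at a treatment-arm contact is not counted.

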7.3.3.3 Six month Booster

A 6-month booster session will also be provided to assist the older adults with any new fall hazards and to reinforce self-management/mindfulness training techniques. To identify additional fall hazards, the occupational therapist will complete the WeHSA with the older adult and make recommendations for solutions or provide additional training.

7.3.3.4 Monthly monitoring falls

To record falls, an individually customized calendar journal will be designed for each participant for daily recording of falls^[48]. Our method of tailoring the calendar journal includes life event date anchors, incentives and personalization^[49], we will construct the participant-tailored calendar journals^[50]. There will be space to record the primary outcome of falls (fall or no fall) each day. If a participant falls, they will be instructed to complete a fall form. Calendar journal pages and fall forms will be collected monthly via U.S. mail. Falls will be verified with a follow-up telephone interview by a community coordinator.

7.3.3.5 Raters

Follow up assessments will be conducted by trained raters blind to group allocation. The follow-up sessions will repeat assessments conducted at the first study home visit and first phone call.

7.3.4 Completion/Final Evaluation

List each assessment to be performed at the participant's final visit.

Falls behavioral Scale for Older People (FaB). Protective behavioral factors to prevent falls will be assessed using the FaB. This instrument includes ten behavioral dimensions: cognitive adaptations, protective mobility, avoidance, awareness, pace, practical strategies, displacing activities, being observant, changes in level, and getting to the phone^[66].

OARS ADL scale. The OARS ADL scale^[51] will be used to screen for functional performance. The OARS ADL has been validated for the older adult ED population^[52], is brief and easy to administer. Potential participants are asked about their ability to perform each of 14 activities. Responses are scored on a 0-2 scale, with higher scores indicating greater independence. Individuals who receive a score of 0 on one or more activities or a score of 1 on two or more activities will qualify for the study.

Falls Efficacy Scale-International (FES). The Falls Efficacy Scale-International (FES-I)^[53] will be used to assess participants' self-efficacy in performing daily activities without falling. The FES-I has good test-retest reliability and validity and consists of a list of 16 daily activities (e.g., getting in and out of bed) on which respondents rate their confidence doing each activity without falling on a scale from 1 (very confident) to 10 (no confidence at all). Total FES-I score is the sum of each activity score, with higher scores indicating greater fear of falling.

Patient Reported Outcomes Measurement Information System (PROMIS) Global Scale. Self-rated health will be measured using the Patient Reported Outcomes Measurement Information System (PROMIS) Global Scale^[54] which measures general perceptions of health. We will use two scales: global physical health (overall physical health, physical function, pain, and fatigue) and global mental health (quality of life, mental health, satisfaction with social activities, and emotional problems). Reliability and validity of the scales have been established^[54, 55].

7.4 Process evaluation

7.4.1 Recruitment

Enrollment and retention will be tracked by the research coordinator using REDCap, an online data entry program. Recruitment information for each participant will include the potential participants' initials, gender, birthdate, race, zip code, stroke date, admission date, and discharge date. Reasons for denying participation in the study as well as study attrition will also be tracked via REDCap.

7.4.2 Fidelity

In order to guarantee treatment fidelity, or our ability to provide the same treatment as planned to each participant, we follow similar methods of Weersing, et al^[36] and use a Visit by Visit Treatment Grid. This grid specifically outlines the pre, during, and post treatment visit requirements for each treatment session. It is designed to be a checklist in which therapists check off the action once it is completed. During weekly interventionist meetings, the lead therapist will review the treatment grid for each participant to guarantee the necessary components of the intervention are being delivered.

